7.2.5.1. Statistical Methodology Specification

Endpoint / Variables

 Number (%) of subjects with mean Hgb in the target range (11.0-13.0 g/dL) during the primary efficacy evaluation period (Week 40 to 52)
Model Specification

 The percentage of subjects with observed mean Hgb during the primary efficacy evaluation period within target range will be derived from the mean of observed Hgb values during the primary efficacy evaluation period for individuals. Analyses will be conducted by a logistic regression model as follows: $\text{logit}(\pi) = \beta_0 + \beta_{\text{baseline}} * \text{Baseline}_i + \beta_j + \beta_l + \varepsilon$ 
 π_i: treatment success (mean(Hgb_i) is within the target range or not) β_0: Intercept β_{baseline}: baseline Hgb effect Baseline_i: Hgb measurement for subject i β_j: treatment effect (j= daprodustat, epoetin beta pegol) β_l: Prior ESA use effect (l = ESA user, ESA non user) ε: random error i: subject (i = PPD ..., N) N: number of subjects included in the analysis The mean Hgb during the primary efficacy evaluation period will be calculated by individuals and confirmed if the values are in the target range or not. Therefore, subjects who have at least one Hgb measurement during the evaluation period will be included in this analysis. A subject who has missing data of the mean Hgb during the primary efficacy evaluation period due to intercurrent events will be regarded as a non-responder. The odds ratio (daprodustat/epoetin beta pegol) will be obtained as follows: $\text{OR} = \exp(\beta_{\text{daprodustat}} - \beta_{\text{epoetin}})$ The odds ratio, the Wald-type 95% CI. and a superiority one-sided p-value based on a z-score will be provided together.
Model Checking & Diagnostics

 If the logistic regression cannot be applicable due to all responders or all non-responders, the odds ratio and the associated statistics will not be provided. If there is a problem with quasi-complete separation, a penalized likelihood method by Firth will be used by specifying the FIRTH option in the MODEL statement.

Model Results Presentation

- The superiority assessment will be performed only if the primary endpoint achieved non-inferiority.

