The time (weeks and percent) within/above/below the target range will be summarized by treatment group using mean, standard deviation, minimum, P25, median, P75, and maximum. For the ITT population, the treatment differences (daprodustat – epoetin beta pegol) and the associated 95% CIs for the time (weeks and percentage) within the target range will also be provided. See Section 15.6.3 for details. The summary will also be provided by prior ESA use.

Time (in days) to reach the lower Hgb target (11.0 g/dL)

The time (days) to reach the lower Hgb target will be summarized by treatment group using P25, median, and P75 by Kaplan-Meier method. Kaplan-Meier plot of time to event will be provided using on-therapy Hgb values including unscheduled visits. Subjects who could not reach lower target will be regarded as censored. Subjects who have baseline central laboratory Hgb ≥ 11.0 g/dL will be excluded in this analysis. The summary will also be provided by prior ESA use.

Number (%) of subjects who have an Hgb level of less than 7.5 g/dL

The number and percentage of subjects who have an Hgb level of less than 7.5 g/dL during the treatment period will be summarized by treatment group. On-therapy Hgb values observed in both scheduled and unscheduled visits will be included in the summary.

Number (%) of subjects who have an Hgb increase of more than 2.0 g/dL over any 4 weeks

The number and percentage of subjects who have an Hgb increase of more than 2.0 g/dL over any 4 weeks (excluding Week 2) during the treatment period will be summarized by treatment group. For the ITT population, the odds ratio (daprodustat/epoetin beta pegol) will also be provided with its 95% CI. On-therapy Hgb values will be used for the summary. See Section 15.6.3 for details.

Number (%) of subjects who have an Hgb level of more than 13.0 g/dL and number of episodes

The number and percentage of subjects who have an Hgb level of more than 13.0 g/dL during the treatment period and number of episodes will be summarized by treatment group. On-therapy Hgb values observed in both scheduled and unscheduled visits will be included in the summary.

Scatter plot of Hgb assessments: Central Laboratory vs. HemoCue

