Hgb (g/dL)	Lab Date	Study Day	Visit	Hgb increase
9.1	PPD	1	Day 1	Not calculated
9.8		30	Week 4	0.7
11.9		61	Week 8	2.1
12.6		127	Week 16	Not calculated
12.7		158	Week 20	0.1
12.3		183	Week 24	-0.4

- Odds ratio and its 95% CI will be obtained using the same statistical model described in Section 7.2.5.
- When the odds ratio is undefined, it will not be presented.

Scatter plot of Hgb assessments: Central Laboratory vs. HemoCue

- All available pairs of Hgb (i.e. non-missing values in both from central laboratory and from the corresponding HemoCue measurement) will be used, regardless of treatment groups and visits. The figure will include a linear regression line with 95% CI band, R-squared, and Pearson's correlation coefficient.

Hgb Values
Scatter plot of Change from Baseline in Hgb at Week 4 vs covariates of interest

 The following scatter plot figures will be produced separately: 
 Change from baseline in Hgb (g/dL) at Week 4 vs. Baseline body weight (kg) Change from baseline in Hgb (g/dL) at Week 4 vs. Baseline Hgb (g/dL) Change from baseline in Hgb (g/dL) at Week 4 vs. Prior ESA dose Different displays by prior ESA use will be used to differentiate them. Vertical axis will indicate the change from baseline in Hgb (g/dL) at Week 4, horizontal axis will indicate the covariates of interest, baseline body weight (kg), baseline Hgb (g/dL), or prior ESA dose (IU/week). Only individual plots will be provided unlike the scatter plot of Hgb assessments.
Scatter plot of Mean Dose during Week 40 to 52 vs. Covariates of Interest

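### The Firth fallback for separated data is paired with Wald limits that are too wide toward 1, and the rapid-rise analysis does not say whether an arm with no events makes the odds ratio undefined

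*SAP*

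**What the plan says.** Section 7.2.5.1 defines the logistic model for the principal secondary endpoint, with treatment, baseline Hgb and prior ESA use. It specifies one form of inference: "The odds ratio, the Wald-type 95% CI. and a superiority one-sided p-value based on a z-score will be provided together". Two contingencies follow:

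- Separation: "If there is a problem with quasi-complete separation, a penalized likelihood method by Firth will be used". Neither the interval nor the test changes with the estimator.
- Non-applicability: if "the logistic regression cannot be applicable due to all responders or all non-responders, the odds ratio and the associated statistics will not be provided". The text does not say whether this means all subjects in the analysis or all subjects in one arm.

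For the rapid-rise endpoint, Section 7.3.2 plans counts and percentages by treatment group and adds: "For the ITT population, the odds ratio (daprodustat/epoetin beta pegol) will also be provided with its 95% CI". Section 15.6.3 gives the method, "Odds ratio and its 95% CI will be obtained using the same statistical model described in Section 7.2.5", and then its own exception: "When the odds ratio is undefined, it will not be presented". It does not define undefined and names no substitute statistic.

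The Revision History (Section 16) records that the separation rule was added because the problem may occur, so the sponsor expects to meet it.

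**The concern.** There are two linked defects.

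**Mismatched inference.** When one treatment-by-outcome cell is empty, the maximum likelihood odds ratio is 0 or infinite. Firth's penalty makes the estimate finite, but the penalized likelihood stays strongly skewed on the log-odds scale. A symmetric Wald interval ignores the skew. Its limit on the side of no difference lies too close to 1, or beyond it. The interval that matches the estimator is the profile penalized-likelihood interval, and the matching test is the penalized likelihood-ratio test.

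**An unclear exit.** An arm with no events is quasi-complete separation on treatment. If Section 15.6.3 imports the whole of Section 7.2.5, Firth gives a finite odds ratio. If *undefined* refers to the maximum likelihood odds ratio, the cell is left blank. Two competent programmers could produce different tables from the same data.

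At stake is the only between-arm statistic planned for the rapid-rise endpoint, and the responder odds ratios in small subgroups, where one arm could reach 100% response.

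**Working it through.** **Inputs.** About 286 ND subjects randomized 1:1 (Section 2.3), so 286 / 2 = 143 per arm. The ITT population leaves out Cohort 1 ESA non-users, so 135 per arm is used as a second, assumed size. The SAP gives no event rate for this endpoint, so all event counts are assumptions. It also states no figure that could be reproduced.

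**Formulas (two arms, no covariates).** Firth's penalty adds 0.5 to each cell:

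- OR = [(k1 + 0.5)(n0 − k0 + 0.5)] / [(k0 + 0.5)(n1 − k1 + 0.5)]
- p = (k + 0.5)/(n + 1) in each arm, and SE(log OR) = √[1/(n1 p1(1 − p1)) + 1/(n0 p0(1 − p0))]
- Wald limits: exp(log OR ± 1.96 SE)
- Profile limits: the values of log OR at which twice the drop in the penalized log-likelihood, maximized over the intercept, equals 3.84

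**Worked example, 6/143 against 0/143.** OR = (6.5 × 143.5)/(0.5 × 137.5) = 13.57, so log OR = 2.608. With p1 = 6.5/144 and p0 = 0.5/144, SE = √(0.162 + 2.021) = 1.478. Wald: exp(2.608 ± 2.896) = 0.75 to 246. The profile limits, found numerically, are 1.58 to 1776.

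**Results at 143 per arm** (two-sided p-values):

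| Events | Firth OR | Wald 95% CI (p) | Profile 95% CI (p) | Fisher p |
|---|---|---|---|---|
| 5 vs 0 | 11.4 | 0.62–210 (0.102) | 1.27–1501 (0.026) | 0.060 |
| 6 vs 0 | 13.6 | 0.75–246 (0.078) | 1.58–1776 (0.013) | 0.030 |
| 7 vs 0 | 15.8 | 0.88–282 (0.061) | 1.89–2054 (0.006) | 0.015 |
| 8 vs 0 | 18.0 | 1.02–318 (0.049) | 2.21–2336 (0.003) | 0.007 |
| 10 vs 0 | 22.6 | 1.30–393 (0.033) | 2.86–2914 (0.0007) | 0.002 |

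At 135 per arm the pattern is the same. For 0 vs 6, Wald gives 0.004–1.33 and the profile 0.0006–0.63. For 0 vs 8 the Wald upper limit is 0.98.

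**With covariates.** Baseline Hgb and prior ESA use were added at 143 per arm, with assumed covariate distributions and 60 simulated data sets per count. The two intervals disagreed about 1 in 97% (5 vs 0), 88% (6 vs 0), 18% (7 vs 0) and 0% (8 vs 0) of data sets.

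**Responder subgroups.** For 40/40 against 34/40, Wald gives 0.80–291 (p = 0.070) and the profile 1.70–2017 (p = 0.010), with Fisher p = 0.026. For 40/40 against 32/40 the Wald interval, 1.14–395, already excludes 1.

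**How often an arm is empty.** P(no events) = (1 − rate)^n. For n = 143: 0.99^143 = 24%, 0.98^143 = 5.6%, 0.97^143 = 1.3%. For a subgroup arm of 25: 78%, 60% and 47% at the same assumed rates.

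**The case against.** A reader might infer that the plan hides the most extreme arm differences or reads them as null. The documents do not support that. The larger the imbalance, the less the Wald interval misleads: from 8 against 0 it excludes 1. Nothing is concealed either, because Section 7.3.2 reports number and percentage by arm and Section 15.10.4.9 lists the subjects with a rapid rise. Only the comparative statistic is affected.

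A reader might also infer that Sections 7.2.5.1 and 15.6.3 flatly contradict each other. They can be read together: the Firth rule comes with the model, and *undefined* then covers only tables with no events, or all events, overall. That reading is reasonable, but the text does not compel it, so the ambiguity remains.

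Other points against the concern stand. At 5 against 0 Fisher's exact test (p = 0.060) sides with Wald at the 5% level. The endpoint covers any 4-week rise from Day 1 to Week 52 and includes ESA non-users whose Hgb is meant to increase, so an empty arm may be uncommon. At 135 per arm the chance of a 0 against 5–7 table is about 12% with assumed rates of 1% and 4%, 3% with 2% and 4%, and 0.8% with 3% and 5%. Section 5.5 treats other secondary endpoints as complementary or exploratory, without multiplicity adjustment, and Section 7.2.5.1 calls the responder subgroups exploratory.

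It might also be inferred that the confirmatory superiority test is at risk. Separation by treatment in the full mITT analysis would need every subject in one arm to be in range, or none. That is unlikely, and in these examples the error would be a missed claim rather than a false one.

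**Conclusion.** The point holds as a mismatch of method plus an undefined term. Wald limits on a Firth estimate are too wide toward 1 under separation. At about 135 to 143 per arm this changes the reading for roughly 5 to 7 events against 0, and Fisher's exact test supports the profile interval from 6 against 0 upward. Outside that band the conclusion about 1 is essentially the same, although the limits still differ.

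The effect is confined mainly to the rapid-rise odds ratio and the responder subgroup odds ratios, which are exploratory. The size rests on assumed event counts and, for the adjusted model, on assumed covariate distributions. The change is still worth making, because the sponsor anticipates separation and the remedy costs almost nothing.

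**What to change.** In Sections 7.2.5.1 and 15.6.3, state that when any treatment-by-outcome cell is zero, or separation is detected, the model is fitted with Firth's penalty, the 95% limits are profile penalized-likelihood limits (CLODDS=PL with the FIRTH option), and any p-value comes from the penalized likelihood-ratio test.

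Keep the sentence in Section 15.6.3 that withholds an undefined odds ratio, but define the term, and NC, as no events or all events in both arms combined. Word the all-responders and all-non-responders rule in Section 7.2.5.1 the same way, so that one empty arm goes to Firth.

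Cost: one or two sentences in the SAP and one SAS option. No new data or displays are needed.

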2.3. Study Design

Overview of Study Design and Key Features	
Screening phase (4 weeks)	Treatment phase (52 weeks) Primary efficacy evaluation period
Follow-up phase (4 weeks)	
Cohort 1 Non-dialysis (ND) subjects	
GSK1278863 group
 
Epoetin beta pegol group

Cohort 2 Peritoneal dialysis (PD) subjects	GSK1278863 group
Cohort 3 Non-dialysis (ND) subjects	
GSK1278863 group
 
Epoetin beta pegol group

Week -4 Week 52	Day 1 Week 56
Week 40	
Design Features	
 • This is a Phase III, open-label, active-controlled, parallel-group, multi-center study to compare the efficacy (verification of noninferiority) and safety of GSK1278863 administered for 52 weeks versus epoetin beta pegol in approximately 286 Japanese ND subjects with renal anemia. • This study also includes an open-label, uncontrolled part to evaluate the efficacy and safety of GSK1278863 in approximately 50 Japanese PD subjects. • Cohort 1 (ND subjects) and Cohort 2 (PD subjects) were set for target population of this study when the study was planned. • Cohort 3 is newly added in amendment (Amendment No. 3). ND subjects will be randomized not to Cohort 1 but to Cohort 3 after amendment No.3.
Dosing	GSK1278863 Starting Dose

Overview of Study Design and Key Features	

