A scatter plot of Hgb values measured by Central Laboratory versus Hgb values measured by Hemocue will be produced along with Pearson's correlation coefficient. Regardless of visit and treatment group, all available pairs of Hgb (i.e. non-missing values in both from central laboratory and from the corresponding HemoCue measurement) will be used.

- **Dose adjustment**

The dose adjustment algorithm is described in Section 15.6.3, based on HemoCue Hgb values.

Dose at each assessment visit / final visit

Dose at each assessment visit and final visit will be summarized by treatment group using mean, standard deviation, minimum, P25, median, P75, mode, and maximum at each assessment visit. The final visit will be the last visit of treatment exposure for each subject. Mean dose during Week 40 to 52 will also be summarized and includes subjects who has at least one exposure record during Week 40 to 52. The summary will also be provided by Prior ESA use, prior ESA dose, prior ESA type, and ERI.

Duration (days) of treatment interruption due to Hgb >13.0 g/dL

The number and percentage of subjects who have a period of treatment interruption due to Hgb >13.0 g/dL will be summarized by treatment group. On subjects who have a period of treatment interruption due to Hgb >13.0 g/dL, the duration (in days) of treatment interruption due to Hgb >13.0 g/dL per subject will be summarized by treatment group using mean, standard deviation, minimum, P25, median, P75, and maximum. On-therapy Hgb values observed in scheduled visits will be counted in the summary. The summary will also be provided by prior ESA use.

Dose adjustment

The number and percentage of subjects with dose adjustments will be provided. Number of dose adjustments will be summarized by treatment group using mean, standard deviation, minimum, median, mode, and maximum. For dose adjustments frequency, the number and percentage of subjects will be provided by the number of dose adjustments (i.e. zero, one, two, three, four, ..., ten, eleven, and twelve or more; may be refined) by treatment group during the whole treatment period. For timing of dose adjustments, the

number and percentage of subjects with dose adjustments by each assessment visit will be provided by treatment group. The summary will also be provided by Prior ESA use.

Dose adjustment to reach the lower Hgb target (11.0 g/dL)

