15.3.1. Definitions of Assessment Windows for Analyses

Analysis Time Point	Definitions
Screening ^[1]	Data collected in Screening visit If multiple records are present, the latest record will be used for analysis.
Day 1 ^[1]	Data collected in Day 1 visit If multiple records are present, the latest record will be used for analysis.
Week 2	Data collected in Week 2 visit ^[2]
Week 4	Data collected in Week 4 visit
Week 8	Data collected in Week 8 visit
Week 12	Data collected in Week 12 visit
Week 16	Data collected in Week 16 visit
Week 20	Data collected in Week 20 visit
Week 24	Data collected in Week 24 visit
Week 28	Data collected in Week 28 visit
Week 32	Data collected in Week 32 visit
Week 36	Data collected in Week 36 visit
Week 40	Data collected in Week 40 visit
Week 44	Data collected in Week 44 visit
Week 48	Data collected in Week 48 visit
Week 52	Data collected in Week 52 visit
Follow-up	Data collected in Follow-up visit

Note:

Any unscheduled visit will not be slotted to a particular time point.

[1] For rescreened subjects, data collected in screening-pass visit (i.e. screening and day 1 visit where the subject has passed a screening test) will be used for analysis. They may have multiple records at Screening and/or Day 1 visit, which associates with a screening pass visit and screening failure visit(s) (see Section [15.6.1](#) and Section [15.6.2](#))

[2] Only ND subjects randomized to Cohort 3

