15.6.3. Efficacy

Hgb Values
Central laboratory and HemoCue Hgb Values

 For reporting purposes, central laboratory Hgb values will be used, unless otherwise specified. However, if a central laboratory Hgb value is missing, a corresponding non-missing HemoCue Hgb value, which is associated with the identical subject number and visit, will be used.
Evaluable Hgb Values

 It will be used for reporting sensitivity analysis results and Hgb listings. Evaluable Hgb values will be based on on-therapy central laboratory and/or HemoCue Hgb values that are not taken within the 8 weeks following a red blood cell transfusion, a whole blood transfusion, or a non-randomized ESA medication which occurs on or after the randomization date (except protocol-specified ESA treatment in screening period). 
If an Hgb record meets at least one following criteria, the Hgb record will be regarded as non-evaluable.
 
 Blood Product Administration Date < Date of Hgb data ≤ Blood Product Administration Date + 56 (days) ESA Start Date < Date of Hgb data ≤ ESA Stop Date + 56 (days)

Hgb Values

Flowchart for Hgb analyses

- This flowchart will be applicable, unless otherwise specified
 - Basically, scheduled visits between Day 1 and Week 52 will be applicable to this flowchart, but analyses including by-visit summaries may include other scheduled visits (ie. screening and follow-up visit).
- [1] Regarding partially evaluated Hgb values, the following summaries of Hgb will include unscheduled visits:
- Summary of Time (weeks and %) within Hgb target range during the primary efficacy evaluation period
 - Summary of Number (%) of subjects who have an Hgb level of less than 7.5 g/dL
 - Summary of Number (%) of subjects who have an Hgb level of more than 13.0 g/dL and number of episodes
 - Time (in days) to reach the lower Hgb target (11.0 g/dL)

Hgb increase of more than 2.0 g/dL over any 4 weeks

- For this reporting purpose, Hgb values from central laboratory will be used as previously described.
- A subject who has at least one record with Hgb increase of more than 2.0 g/dL over any 4 weeks will be counted and all episodes will be listed.
- Hgb increase will be calculated for scheduled visits between Day 1 and Week 52 if available (i.e. Week 4 Hgb - Day 1 Hgb, Week 8 Hgb - Week 4 Hgb, ...)

Illustration of calculation (example in case of Week 12 missing, until Week 24 visit)

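### The 95% band on the central laboratory versus HemoCue Hgb plots makes no allowance for 15 to 16 pairs per subject, so it is too narrow if residuals are positively correlated within subject

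*SAP*

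**What the plan says.** SAP Section 7.3.2 defines the data for the scatter plot: "Regardless of visit and treatment group, all available pairs of Hgb", meaning every pair with both values present. Section 15.6.3 repeats that these pairs "will be used, regardless of treatment groups and visits" and adds: "The figure will include a linear regression line with 95% CI band", together with R-squared and Pearson's correlation. Neither section names a subject effect, a cluster-robust variance, a bootstrap by subject or any other allowance for repeated pairs. The revision history (Section 16) records that Amendment 1 added the line, its band and R-squared.

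The list of efficacy figures (Section 15.10.4.3) has two such plots: Figure 2.28 for ITT and Figure 2.29 for Efficacy PD. The endpoint table in Section 7.3.1 marks the plot as a summary figure, not as a statistical analysis.

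The schedule of activities (Section 15.2.1) has HemoCue Hgb at screening, Day 1, Week 2 and every four weeks from Week 4 to Week 52, with central laboratory Hgb at the same visits. A note in Section 15.3.1 limits the Week 2 visit: "Only ND subjects randomized to Cohort 3".

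**The concern.** A regression band computed in the ordinary way treats each plotted pair as a separate piece of information. Here the pairs come in groups of about 15 from the same person. If the HemoCue reading tends to lie above the central value in some subjects and below it in others, the residuals within a subject move together. The data then carry less information about the line than the number of points suggests, and the plotted 95% band overstates how precisely the line is known. The plan does respect this kind of dependence elsewhere: the primary MMRM (Section 7.1.5.1) uses an unstructured within-subject covariance for Hgb.

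What is at stake is the honesty of one stated error bar. The trial's conclusions are not at stake.

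**Working it through.** The SAP states no width or precision for this band, so there is no figure to reproduce. The check is how far an ordinary band could be off.

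**Pairs per subject.** Screening, Day 1 and the 13 visits from Week 4 to Week 52 give 15 pairs for a completer in Cohorts 1 and 2. Week 2 makes it 16 in Cohort 3. The calculation uses m = 15.

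**Subjects.** Section 2.3 plans the comparison "in approximately 286 Japanese ND subjects with renal anemia", and "approximately 50 Japanese PD subjects" for the uncontrolled part. That is up to 286 × 15 = 4,290 pairs (286 × 16 = 4,576 if all had Week 2) and 50 × 15 = 750 pairs. ITT leaves out Cohort 1 ESA non-users, so the ITT figure may hold somewhat fewer.

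**Relative error at mean Hgb.** Let ρ be the within-subject correlation of the regression residuals. This is not the correlation of Hgb itself, and the SAP does not give it, so a range is assumed. The ratio of correct to ordinary width is √(1 + (m − 1)ρ). Coverage of the ordinary band is 2Φ(1.96/ratio) − 1.

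| ρ (assumed) | 1 + 14ρ | Width ratio | Coverage |
|---|---|---|---|
| 0 | 1.0 | 1.00 | 95% |
| 0.05 | 1.7 | 1.30 | 87% |
| 0.1 | 2.4 | 1.55 | 79% |
| 0.3 | 5.2 | 2.28 | 61% |
| 0.5 | 8.0 | 2.83 | 51% |

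With m = 16 the ratio is 1.32 at ρ = 0.05 and 2.92 at ρ = 0.5.

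**Away from the mean.** Ordinary least squares was simulated on clustered pairs (m = 15, 286 or 50 subjects, 1,500 replicates, within-subject correlation of the Hgb on the horizontal axis 0.2 or 0.4). It agrees with the table at the mean. At 2 SD above the mean the effect is smaller: with 286 subjects the ratio is 1.11 to 1.17 at ρ = 0.05 (coverage 90% to 92%) and 1.87 to 2.17 at ρ = 0.5 (coverage 62% to 71%).

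**Absolute size at mean Hgb.** The ordinary half-width is 1.96 × SD/√(pairs). The residual SD is not in the SAP; 0.5 and 1.0 g/dL are assumed. The corrected value takes ρ = 0.5, the largest in the table.

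- ITT, 4,290 pairs, SD 0.5: 1.96 × 0.5/65.5 = 0.015; × 2.83 = 0.042 g/dL. With SD 1.0: 0.030 and 0.085. The shortfall is about 0.03 to 0.055 g/dL.
- PD, 750 pairs, SD 0.5: 1.96 × 0.5/27.4 = 0.036; × 2.83 = 0.10 g/dL. With SD 1.0: 0.072 and 0.20. The shortfall is about 0.065 to 0.13 g/dL.

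For scale, the non-inferiority margin is 1.0 g/dL and the target range, 11.0 to 13.0 g/dL, is 2 g/dL wide.

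**The case against.** The strongest objection is that this hardly matters. The band describes the mean line, not how closely single readings agree. With thousands of points even a corrected ITT band is nearly a line, and a coverage of 51% sounds worse than a shortfall of hundredths of a g/dL. The plot is a descriptive summary and nothing is decided from it. This stands, and it sets the weight of the point.

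A second objection is that the SAP does not name the variance method, and the display shells are in a separate document (Section 15.11). That is true. But the SAP sections that define the figure pool all pairs and ask for a regression band without qualification, and the plain reading of that is an ordinary band.

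A third is that the direction of the error rests on an assumption. This also stands: at ρ = 0 the band is correct. With 15 pairs per subject, though, even 0.05 brings coverage down to about 87%.

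A reader might go further and take these figures as the plan's evidence that HemoCue can stand in for the central laboratory, since HemoCue guides dose adjustment and Section 15.6.3 lets it replace missing central values: "if a central laboratory Hgb value is missing, a corresponding non-missing HemoCue Hgb value" is then used. The SAP does not support that reading. It nowhere gives the figures that purpose, and the substitution rule applies whatever the plot shows.

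**Conclusion.** The point holds as a minor correction. As written, the 95% band in Figures 2.28 and 2.29 ignores repeated pairs, and it is too narrow whenever residuals are positively correlated within subject. For assumed correlations of 0.05 to 0.5, the understatement at mean Hgb is a factor of 1.30 to 2.83, less towards the ends of the Hgb range. Both the correlation and the residual SDs behind the absolute sizes are assumptions.

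It would be wrong to infer that the band is known to be too narrow, or that the primary or principal secondary result is affected. The SAP gives no residual correlation, and neither analysis uses the figure or its band.

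**What to change.** In Section 15.6.3, state that the band will use a variance clustered by subject (robust, or a bootstrap that resamples subjects), or remove the band. Apply the same choice to both figures. The fitted line, R-squared and Pearson's correlation can remain as descriptive summaries of the pooled pairs.

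A clustered band costs some added programming and is slightly wider on the page; removing the band costs almost nothing. A mean difference between methods with limits of agreement would be a further analysis that the team may like to have, but it is a preference and is not needed to correct this error.
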